### **8.6 Study Drug Accountability**

Records shall be maintained of the delivery of study treatment(s) to the study site(s), of the inventory at the study site(s), of each use of the study treatment(s) for each patient, and of the return of unused study treatment(s) to Albireo.

These records shall include dates, quantities, batch numbers, expiry dates, and the unique code numbers assigned to the study drug and to the study patients.

The investigator will be responsible for ensuring that the records adequately document that the patients were provided the quantities specified in the protocol and that all study drug received from Albireo is reconciled.

### **8.7 Concomitant Therapy and Prohibited Medications**

The investigator will note all ongoing medication and any medication recently stopped (within 1 month prior to Visit 1) in the eCRF. At Visits 2 through 10, all changes in medication (stopping or starting new medication or changes in dose) will be recorded in the eCRF. All medications (prescribed or over the counter) for pruritus and sleep will be recorded.

All medications taken by a patient within 3 months prior to the first intake of study drug are regarded as prior medication.

All medications taken by a patient on or after the first intake of study drug, and which continue to be taken during the study, are regarded as concomitant medication.

Prohibited medications are listed in [Appendix 1](#).

## 9 ASSESSMENT OF EFFICACY

### 9.1 Efficacy Endpoints

#### 9.1.1 Primary Efficacy Endpoint

The primary efficacy endpoints are as follows:

- **European Union (EU) and rest of the world (RoW):** Proportion of patients experiencing at least a 70% reduction in fasting s-BA concentration from baseline to the end of treatment or reaching a level  $\leq 70$   $\mu\text{mol/L}$  compared to placebo after 24 weeks of treatment.

Fasting s-BA baseline will be calculated as the average of the value at randomization and the previous visit (Clinic Visit 2). The end value is the average of the values at Weeks 22 and 24 after the start of double-blind treatment.

- **United States (US):** Proportion of positive pruritus assessments at the subject level over the 24-week Treatment Period. A positive pruritus assessment is defined as a scratching score of  $\leq 1$  or at least a one-point drop from baseline on the Albireo ObsRO instrument. At each assessment, the AM score will be compared to the baseline AM average, and the PM score will be compared to the baseline PM average. Both AM and PM pruritus assessments will be included in the analysis of this endpoint. AM scores from the 14 days prior to the first dose of study medications will be averaged as AM baseline. PM scores from the 14 days prior to the first dose will be averaged as PM baseline.

#### 9.1.2 Secondary Efficacy Endpoint

Secondary efficacy endpoints include the following:

- **EU and RoW:** Proportion of positive pruritus assessments at the subject level over the 24-week Treatment Period. A positive pruritus assessment is defined as a scratching score of  $\leq 1$  or at least a one-point drop from baseline on the Albireo ObsRO instrument. At each assessment, the AM score will be compared to the baseline AM average, and the PM score will be compared to the baseline PM average. Both AM and PM pruritus assessments will be included in the analysis of this endpoint. AM scores from the 14 days prior to the first dose of study medications will be averaged as AM baseline. PM scores from the 14 days prior to the first dose will be averaged as PM baseline.
- **US:** Proportion of patients experiencing at least a 70% reduction in fasting s-BA concentration from baseline to the end of treatment or reaching a level  $\leq 70$   $\mu\text{mol/L}$  compared to placebo after 24 weeks of treatment.
- **All Regions:**

All secondary endpoints are compared to placebo.

- Change from baseline to Week 12 and to Week 24 in fasting serum bile acids
- Change from baseline to Week 12 and to Week 24 in serum ALT concentration
- Change in growth from baseline to Week 12 and to Week 24
- Proportion of responders for pruritus scores at Weeks 12 and 24 based on the Albireo PRO and ObsRO instruments
- Change in sleep parameters measured with the Albireo PRO and ObsRO instruments from baseline over the 24-week Treatment Period
- Proportion of individual assessments meeting the definition of a positive pruritus assessment at the subject level over the 24-week Treatment Period. A positive pruritus assessment includes an itch score  $\leq 1$ , or at least a one-point drop from baseline based on the Albireo PRO instrument; only patients  $\geq 8$  years of age will complete the Albireo PRO instrument
- Proportion of individual assessments meeting the definition of a positive pruritus assessment at the subject level from Weeks 0-4, Weeks 0-8, Weeks 0-12, Weeks 0-18, Weeks 0-24, respectively, or the proportion of positive pruritus assessments at each 4-week interval.
- Proportion of individual AM assessments meeting the definition of a positive pruritus assessment at the subject level from Weeks 0-4, Weeks 0-8, Weeks 0-12, Weeks 0-18, Weeks 0-24, respectively, or the proportion of positive pruritus assessments at each 4-week interval.
- Proportion of individual PM assessments meeting the definition of a positive pruritus assessment at the subject level from Weeks 0-4, Weeks 0-8, Weeks 0-12, Weeks 0-18, Weeks 0-24, respectively, or the proportion of positive pruritus assessments at each 4-week interval.
- Number of patients undergoing biliary diversion surgery or being listed for liver transplantation

### 9.1.3 Exploratory Efficacy Endpoints

Exploratory efficacy endpoints are compared to placebo and include the following:

- Assessment of Global Symptom Relief at Weeks 4, 12, and 24 as measured by patient, caregiver, and clinician via the PGIC items ([Appendix 3](#))
- Change from baseline in fasting s-BA at Week 4

- Change in pruritus, as indexed by caregiver-reported observed scratching, from baseline by each 4 week-interval of the Treatment Period as measured by the Albireo ObsRO instrument
- Change from baseline by each 4-week interval of the Treatment Period in patient-reported and observer-reported night time itching and scratching severity scores, respectively
- Change from baseline by each 4-week interval of the Treatment Period in patient-reported and observer-reported morning time itching and scratching severity scores, respectively
- Change from baseline by each 4-week interval of the Treatment Period in pooled pruritus score including observer-reported scratching for patients <8 years of age and patient-reported itch severity for patients  $\geq 8$  years of age
- Change from baseline by each 4-week interval of the Treatment Period in additional patient-reported and observer-reported sleep parameters (e.g., tiredness and number of awakenings)
- Change from baseline to Week 24 in PedsQL ([Appendix 4](#))
- Change from baseline in serum ALT concentration at Week 4
- Change from baseline in total bilirubin at Weeks 4, 12, and 24
- Change from baseline in AST and GGT at Weeks 4, 12, and 24
- Change from baseline for other biochemical markers and measures of bile acid synthesis (autotaxin, p-C4) at Week 24
- Change in pediatric end-stage liver disease/model for end-stage liver disease (PELD/MELD) score, AST to platelet ratio index (APRI) score, and Fib-4 score from baseline to Week 24
- Change from baseline to Week 24 in stage of liver fibrosis as assessed by Fibroscan® (where available)
- Liver-related mortality and liver decompensation events
- All-cause mortality

## 9.2 Efficacy Assessments

### 9.2.1 Serum Bile Acids

Blood samples for analysis of fasting total s-BA will be drawn at all visits. Patients will fast (water intake only is permissible) for at least 4 hours prior to the collection of samples for s-BA. Exceptions can be made for infants, <12 months of age, if unable to fast for the full 4 hours. Any visit at which a bile acid sample result is unreportable, an additional unscheduled visit for a repeat sample collection may be scheduled. All s-BA results during

the treatment period and follow-up will be blinded. Samples will be processed and transported to a central laboratory per instructions in the laboratory manual.

### **9.2.2 Itching, Scratching and Sleep Score**

Itching, observed scratching, and sleep disturbance will be recorded twice each day via eDiary. Patients and/or caregivers will be instructed to complete the eDiary every day in the morning after the patient wakes and in the evening just before the patient goes to sleep throughout the study. Patients and caregivers will receive a formal training session during Visit 1.

The eDiary includes Albireo ObsRO and PRO items. Patients <8 years of age will not be asked to complete the Albireo PRO items; only the Albireo ObsRO will be completed by caregivers of patients in this age group. Older patients, 8 to 18 years of age, will complete the Albireo PRO items and the caregiver will complete the Albireo ObsRO items. The Albireo PRO items assess severity of itch, aspects of sleep disturbance (morning diary only), and tiredness. For patients 8 to 12 years of age, the caregiver will read the Albireo PRO items along with the child and record the child's response. A guide will be provided to the caregivers that provides standardized explanations of the Albireo PRO items, in case the patient is confused or requires clarification about the meaning of a question. The Albireo ObsRO items assess severity of observed scratching, aspects of observed sleep disturbance (morning diary only), and observed signs of tiredness (evening diary only). The Albireo ObsRO and PRO scratching and itch severity items use 0 to 4 response scales, where each response is distinguished by a unique facial expression, verbal anchor, number, and color code ([Appendix 2](#)). To meet eligibility criteria, a scratch score will be calculated from daily diary entries (ObsRO items) the 14 consecutive days prior to randomization.

A daily AM & PM score for the Albireo ObsRO scratching item will be averaged from the 2 ratings for each day. A daily score will be considered missing if both of the daily assessments are missing. A weekly score will be calculated by averaging the daily scratching scores. A weekly score will be considered missing if  $\geq 4$  out of 7 days a week of data are missing. For AM & PM baseline, a 14-day daily score of AM & PM prior to the first dose of study medications will be averaged as the baseline score.

For AM baseline, a 14-day AM score prior to the first dose of study medications will be averaged as the baseline AM score. The same approach will be used for PM baseline and to calculate a patient-reported itch severity score. The handling of missing data is described in [Section 11.2.2.2](#).

### **9.2.3 Growth**

Growth will be measured as height (velocity) and weight (Z-score) using a certified weight scale. BMI will be calculated by weight (kg) / height (m). Change will be defined as linear growth deficit (weight and BMI for age) compared to a standard growth curve (Z-score, SD from P50).

#### 9.2.4 Quality of Life Questionnaire (PedsQL)

Patients and caregivers will be asked to complete a QoL questionnaire (PedsQL) at Visit 3 and Visit 9. Details of the questions included on the questionnaire are provided in [Appendix 4](#).

#### 9.2.5 Biomarkers and PK Samples

Blood samples for autotaxin and p-C4 will be drawn at Visits 3, 4, and 9 only for children with body weight >10 kg. Blood for A4250 PK assessment will only be drawn at Visits 4 and 9 (only for children with body weight >10 kg), and as close to the onset of an SAE as possible, should an SAE occur. Samples will be processed and transported to a laboratory per instructions in the laboratory manual.

#### 9.2.6 PELD/MELD Score

At randomization and end of treatment, PELD score will be calculated for children up to 12 years of age. For children 13 years or older, the MELD score will be calculated.

PELD Score =  $4.80 * \ln(\text{total bilirubin}) + 18.57 * \ln(\text{INR}) - 6.87 * \ln(\text{albumin}) + 4.36$  (if patient <1 year: scores for patients listed for liver transplantation before the patient's first birthday continue to include the value assigned for age (<1 year) until the patient reaches the age of 24 months) + 6.67 (if the patient has growth failure [ $\leq 2$  SD])

Laboratory values less than 1.0 will be set to 1.0 for the calculation of the PELD score.

MELD Score =  $9.57 * \ln(\text{creatinine}) + 3.78 * \ln(\text{total bilirubin}) + 11.2 * \ln(\text{INR}) + 6.43$

Laboratory values less than 1.0 will be set to 1.0 and serum creatinine values greater than 4.0 mg/dL (equivalent to 353.6  $\mu\text{mol/L}$ ) will be set to 4.0 for calculation of the MELD score.

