#### **Study Day 154/Clinic Visit 8**

The following procedures and assessments will be performed:

- Review of concomitant medications
- Vital signs ([Section 10.2.6](#))
- Albireo PRO/ObsRO eDiary review for compliance
- s-BA ([Section 9.2.1](#))
- INR
- Urine pregnancy test for girls who have reached menarche
- AE monitoring
- Evaluation of study drug compliance
- Study drug is dispensed

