## **10.2 Laboratory Values/Vital Signs/Physical Examinations and Other Safety Assessments**

### **10.2.1 Laboratory Assessments**

Samples will be collected for clinical chemistry, hematology, and urinalysis testing at the time points specified in [Table 1](#). The parameters assessed are presented in [Table 3](#).

Blood for AFP will be drawn at Visits 3 and 9. Fat-soluble vitamin levels including vitamins A and E, and 25-hydroxy vitamin D will be drawn at Visit 2 (vitamins A & E only), Visit 3 (25-hydroxy vitamin D only), Visit 6, and Visit 9. Blood for INR (surrogate for vitamin K) will be drawn at Visits 2, 4, 6, 8, and 10. Patients will fast (water intake only is permissible) for at least 4 hours prior to the collection of samples for vitamin A. Exceptions can be made for infants, <12 months of age, if unable to fast for the full 4 hours. If a patient has any vitamin level(s) that are outside of the reference range, vitamin supplementation adjustments may be required. Target ranges and supplementation strategy guidelines can be found in [Appendix 5](#).

A serum pregnancy test will be performed at Visit 1 and Visit 9 if the patient is entering the A4250-008 study. A urine pregnancy test will be collected at all other visits for girls who have reached menarche. If a urine pregnancy test is positive, a serum pregnancy test should be performed to confirm the pregnancy. Study drug administration will be held pending the confirmatory results. If the serum pregnancy test is negative, the patient can resume dosing. If the serum pregnancy test is positive, the patient should be discontinued (see [Section 10.2.9](#)).

All samples will be processed and transported to a laboratory per instructions in the laboratory manual.

The observed values will be recorded and assessed as “normal” or “abnormal not clinically significant” or “abnormal clinically significant”.

Additional safety blood samples may be needed due to follow-up of an abnormal value or analysis failure. The blood samples collected for safety laboratory analysis will be destroyed after the analyses have been completed.

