## Scientific Affairs Estimated Blood Volume Request

Version: 11.0

SPONSOR: Albireo

Protocol#: A4250-005

6 mon h to 18 yrs of age

Visit^	Testing 	Tube volume (mL)	Tube Type	# of Collection Tubes	# of Aliquots	Volume (mLs)	Volume/visit (mL)	Volume /visit (tsp)	Volume /visit (TBS)
	Bile Acids, Total 	1.1	SST	1	2	1.1			
	Vitamins, A, E 	2.5	SST	1	1	2.5			
	Vitamin D,25OH	1.1	SST	1	1	1.1			
	PK	1.1	Plasma	1	2	1.1			
							10.3	2.09	0.70
Visit 10 Follow-Up Study Day 196 ± 3	Chemistry	1.1	SST	1	1	1.1			
	Hematology	1.0	EDTA	1	0	1.0			
	Coagulation (INR/PT)	1.4	NaCit	1	1	1.4			
	Bile Acids, Total 	1.1	SST	1	2	1.1			
							4.6	0.93	0.31
Study Total Volume*							57.0	11.6	3.9

^ Visit Schedule and testing based on CLW v1 09

\*Total Volume reflects the volumes required for testing by ICL and 3rd Parties as defined in the test list above

- Notes: #1 Bile Acids, Total, Vitamin A, and Vitamin E testing at ARUP Lab, USA  
 #2 Optional sample Only collected if required  
 #3 hCG is an optional sample, collected if patient is female and of child bearing potential  
 #4 C4 will be performed on plasma sample at LGC  
 #5 The following absolute 'minimum' volume does not allow for repeat testing:  
     Chemistry, AFP requires minimum – 500uL serum  
     Bile Acids requires minimum – 500uL serum  
     Coagulation (PT/INR only) requires minimum – 900uL plasma  
 #6 Sites must collect Full Draw and measure exact aliquot of sample into a "False Bottom" transport tube  
 #7 Autotaxin serum samples will go to LGC lab for testing Optional sample Collected if subject meets weight/age/medical history criteria for collection  
 #8 For subjects requiring optional pregnancy testing, collect 1.1mL SST  
 #9 PK will be performed on plasma sample at LGC

Created by: [name], Protocol Review  
 Date: 14-May-18

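### PELD/MELD is scored at randomization and end of treatment, but INR is scheduled at neither visit and no rule names the end-of-treatment value; the growth-failure cut-off is also printed without its minus sign.

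*Protocol*

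**What the plan says.** Section 9.2.6 fixes the timing: "At randomization and end of treatment, PELD score will be calculated for children up to 12 years of age". Children of 13 years or older get MELD instead. INR enters PELD with coefficient 18.57 and MELD with coefficient 11.2, both on the natural-log scale. Section 9.1.3 lists the resulting exploratory endpoint, "Change in pediatric end-stage liver disease/model for end-stage liver disease (PELD/MELD) score", from baseline to Week 24.

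On sampling, section 10.2.1 says: "Blood for INR (surrogate for vitamin K) will be drawn at Visits 2, 4, 6, 8, and 10". The INR row of Table 1, the visit-by-visit lists in 7.1.3 and the tube list in Appendix 7 all give the same five visits. The lists for Visit 3 and Visit 9/EOT contain no INR.

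PELD also adds 6.67 points "if the patient has growth failure". The bracket that follows defines this as at most 2 SD, with no minus sign. Section 9.2.3 measures growth as a Z-score, in SD from the 50th percentile.

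Section 9.2.6 also sets laboratory values below 1.0 to 1.0. It names no unit for bilirubin or albumin. The protocol version dated 15 March 2018 gave mg/dL and g/dL in the same formulas.

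**The concern.** A score defined at two visits needs all its inputs at those visits, or a rule for which other value to use. Bilirubin, albumin and creatinine belong to the chemistry panel, which is drawn at both visits. INR is the only laboratory input missing. A later analysis plan can choose which INR to carry, but it cannot supply a sample that was never scheduled.

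The substitute is also not guaranteed to be neutral. Appendix 5 suggests vitamin K supplementation when INR is above target, so a raised value at Visit 8 may be acted on before Visit 9, and no INR is scheduled at Visit 9 to record the result.

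The growth term is a different kind of fault: the protocol states a scoring condition and states it wrongly. If programmed as printed, the term no longer separates children with growth failure from the rest.

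**Working it through.** **1. Is the INR tube really absent at the scoring visits?** Appendix 7 gives tube volumes by visit; the coagulation (INR/PT) tube is 1.4 mL.

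- Visit 3: 1.1 + 1.0 + 1.2 + 1.2 + 1.1 + 1.1 = 6.7 mL, as stated.
- Visit 9: 1.1 + 1.0 + 1.2 + 1.2 + 1.1 + 2.5 + 1.1 + 1.1 = 10.3 mL, as stated.
- All visits: 57.0 mL, as stated.

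The stated volumes are reproduced exactly with no coagulation tube at Visit 3 or Visit 9. The tube appears only at Visits 2, 4, 6, 8 and 10, so the gap is not a typing slip in one table.

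**2. How old is the nearest earlier INR?** Days are from Table 1.

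- Randomization: Visit 2 is 7 to 28 days earlier (5 to 30 with its window of 2 days).
- Completers at Visit 9: 168 - 154 = 14 days (8 to 20 with both windows of 3 days).
- Early withdrawal just before Visit 8: the last scheduled INR is from Visit 6, so up to about 154 - 84 = 70 days.

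**3. What is a difference in INR worth?** PELD shift = 18.57 × ln(ratio); MELD shift = 11.2 × ln(ratio). The protocol gives no figure for INR drift between visits, so these INR values are assumptions chosen to show a range.

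| INR at draw and at scoring visit | PELD | MELD |
|---|---|---|
| 1.0 and 1.1 | 1.77 | 1.07 |
| 1.0 and 1.2 | 3.39 | 2.04 |
| 1.1 and 1.4 | 4.48 | 2.70 |

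**4. Who meets the growth condition?** Take Z as normal with SD 1. Mean 0 is a reference population; the lower means are assumed, to represent a growth-impaired one.

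| Mean Z | P(Z ≤ +2), as printed | P(Z ≤ -2) |
|---|---|---|
| 0 | 97.7% | 2.3% |
| -1 | 99.9% | 15.9% |
| -1.5 | 99.98% | 30.9% |
| -2 | about 100% | 50% |

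In the reference population the mean contribution of the term is 6.67 × 0.977 = 6.52 points as printed, against 6.67 × 0.023 = 0.15.

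**5. Do the units matter?** Section 10.2.2.1 equates 3 mg/dL of bilirubin with 51.3 µmol/L, a factor of 17.1. In PELD this factor is worth 4.80 × ln(17.1) = 13.6 points. A constant factor cancels in a change score. The floor at 1.0 does not, because which values it catches depends on the unit.

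**The case against.** The case against making much of this is good, and several parts of it stand.

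- **Baseline is covered.** Section 11.2.2.1 takes the last assessment before first intake unless otherwise specified, so the Visit 2 INR serves. A reader might infer that a child given vitamin K under exclusion criterion 11 has a baseline INR from before the correction. The documents say otherwise: such a child may be randomized on a resample, which follows the vitamin K and precedes dosing.
- **Completers are not far off.** Their INR is nominally two weeks old.
- **Early withdrawals with liver decline are not left without INR.** That reading is tempting, but 10.2.2.1 requires repeat PT or INR within 2 to 3 days, or 48 to 72 hours, once its criteria are met, and 10.2.2.5 adds weekly monitoring after permanent discontinuation for safety. The gap concerns withdrawals without a liver signal. Visit 10 does include INR, but 28 days after the last dose and only for those not entering the extension.
- **The growth bracket only glosses the words growth failure.** A sensible scorer would not award the points to a child at +1 SD, and the sign may have been lost in reproduction. The same form does appear in the two earlier versions of 9.2.6 in the file.
- **A near-constant 6.67 cancels in change from baseline**, which is the endpoint.
- **The analysis is exploratory and descriptive**, and 11.2.2.6 leaves further detail to the SAP.

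What does not fall away is that no end-of-treatment rule exists in the protocol, that no INR is scheduled at that visit, and that the printed cut-off is wrong as a scoring rule.

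**Conclusion.** The point holds as a minor one. As scheduled, end-of-treatment PELD/MELD must combine Visit 9 chemistry with an INR that is nominally 14 days old in completers and up to about 70 days old in some early withdrawals. An INR difference of 1.0 to 1.1 would move PELD by 1.8 points and one of 1.1 to 1.4 by 4.5; both are illustrations, not estimates of actual drift.

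The growth cut-off as printed would give the 6.67 points to about 98% of a reference population instead of about 2%. This rests on reading it literally on the Z-scale of 9.2.3 and on a normal distribution. Its effect is to inflate absolute scores and hide moves into or out of growth failure. A reader might infer that it biases the change endpoint by 6.67 points; the documents do not support that, because the term cancels for nearly every child. Nor do they support saying that the scores cannot be computed, or that the primary or secondary analyses are affected.

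**What to change.** Keep all existing INR draws and add a 1.4 mL INR tube at Visit 9/EOT (10.3 + 1.4 = 11.7 mL), and ideally at Visit 3 (6.7 + 1.4 = 8.1 mL). Amend Table 1, the visit lists in 7.1.3, section 10.2.1 and Appendix 7 to match. Relocating the Visit 8 draw instead would be worse: it would leave no scheduled INR from Day 84 to Day 168, which is 84 days.

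In 9.2.6, print the growth-failure cut-off as ≤ -2 SD, name the growth measure it refers to, and restore mg/dL and g/dL so that the floor of 1.0 is applied on the intended scale.

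The cost is 1.4 mL more blood at each of one or two visits that already have a draw (57.0 mL in total becomes 58.4 or 59.8 mL), plus text edits.
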